16.3. Appendix 3: Assessment Windows

No assessment windows will be applied.

16.4. Appendix 4: Study Phases and Treatment Emergent Adverse Events

16.4.1. Study Phases

Study Phase	Definition
Pre-Treatment	Date ≤ Study Treatment Start Date
On-Treatment	Study Treatment Start Date < Date

Some datasets include the first dosing day as On-Treatment and some exclude the first dosing date as On-Treatment. The first dosing day (Day 1) is considered Pre-Treatment for ECOG, ECG, vital signs, liver events, lab tests, cardiac scan, and other safety domains. The first dosing day (Day 1) is considered to be On-Treatment for adverse events and concomitant medications.

16.4.1.1. Study Time Periods for Concomitant Medications and Blood and Blood Supportive Care Products

Concomitant Medication and Blood and Blood Supportive Care Product start and end dates will be assigned to study time periods in relation to first dose of study treatment as defined below. The start date references time flag variables and end date reference time flag variables will be added to the concomitant medications and blood and blood supportive products datasets, respectively.

- **Start relative to treatment:** Assign to 'BEFORE' if start date is prior to study treatment start date or if subject has not taken any study treatment or (start date is missing and end date is before study treatment start date). Else assign to 'DURING' if the start date falls into the on-therapy period as defined above or if subject is ongoing (not all study treatment discontinuation records completed) or start date is missing. Else assign to 'AFTER' if start date is after the on-therapy period.
- **End relative to treatment:** Assign to 'BEFORE' if end date is prior to study treatment start date or if subject has not taken any study treatment. Else assign to 'DURING' if start date falls into the on-therapy period or if subject is ongoing (not all study treatment discontinuation records completed) or (end date is missing and start relative to treatment not 'AFTER'). Else assign to 'AFTER' if start date is after the on-therapy period or (end date is missing and start relative to treatment='AFTER').

Only on-therapy blood and blood supportive care products that start after the start of study treatment are included in the Blood Products and Blood Supportive Care Product summaries. Therefore, for summary tables, include blood and blood supportive care product records where start relative to treatment in ('DURING') and end relative to treatment in ('DURING', 'AFTER'). All data will be reported in listings.

Concomitant medication start relative to treatment and end relative to treatment flags are used to select data to include in the Concomitant Medication summaries as follows:

- **Summary of Concomitant Medications:** This summary will contain medications including those with start date prior to study treatment start date and continue

(missing end date or end date after study treatment start date) on therapy. Note that any medications with start date and end date prior to study treatment start date will be excluded. In addition, any medication that was started during post-therapy will be excluded. Include concomitant medication records where start relative to treatment in ('BEFORE','DURING') and end relative to treatment in ('DURING','AFTER').

- Summary of Concomitant Medications with On-Therapy Onset: This summary will contain medications with start date after study treatment start date. In addition, any medication that was started during post-therapy (see above for definition of post-therapy) will be excluded. Include concomitant medication records where start relative to treatment in ('DURING') and end relative to treatment in ('DURING','AFTER').

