5.2. Baseline Definitions

For all endpoints (except as noted in baseline definitions) the baseline value will be the latest pre-dose assessment with a non-missing value, including those from unscheduled visits. If time is not collected, Day 1 assessments are assumed to be taken prior to first dose and used as baseline.

For subjects who did not receive study treatment during the study, baseline will be defined as the latest, non-missing collected value.

For ECG analyses, subject level baseline is defined as the mean of triplicate baseline assessments.

Unless otherwise stated, if baseline data is missing no derivation will be performed and baseline will be set to missing.

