Serum (cytokines/chemokines)		X ¹⁹	X			X ¹⁹	At predose and EOI on D1 of each cycle	X	
Serum (anti-drug-antibodies)	X					X ²⁰	At the start of cycles 3 ²⁰ , 6 ²⁰ , 9 ²⁰ , 12 ²⁰ and 16 ²⁰	X	
Plasma-cfDNA	X							X	
Peripheral blood (flow for TBNK)	X ¹⁵					X ¹⁵	At the start of each cycle ¹⁵	X ¹⁵	
Serial Pharmacokinetics (blood)		X ²¹	X ²¹	X ²¹	X ²¹	X ²¹	C3D1 only ²¹	X ²²	
Urine PK	X ²³					X ²³	Day 1 of cycles 4 ²³ , 7 ²³ , 10 ²³ , 13 ²³ , 16 ²³		
Premedication if needed		X				X	At the start of each cycle		
GSK2857916 administration		X ²⁴				X ²⁴	X ²⁴		
Steroid eye drops		X ²⁵				X ²⁵	X ²⁵		
Adverse Events							Continuous		

Time and Events Table for Full Study (Cycle = 21 days)									
Study Assessments ¹	Screen ²	Day 1 C1	Day 2 C1	Day 8 C1	Day 15 C1	Day 1 C2	D1 of C3-C16	End of Study Treatment	3-Month Off-study Follow-up
Concomitant Medications	X	Continuous							
Survival Status									X ²⁶
Subsequent Treatment									X ²⁶

- Assessments scheduled on days of dosing should be done prior to drug administration, unless otherwise specified. All other assessments can be ± 3 days of scheduled occurrence unless otherwise specified.
- All Screening assessments must be performed within 14 days prior to first dose unless otherwise specified. Informed Consent must be signed before any study-specific assessments are performed.
- Screening examination to include BCVA (best-corrected visual acuity), slit lamp examination (with special focus on cornea), intraocular pressure, and dilated fundoscopic examination may be performed within 21 days prior to first dose.
- On-study exams to include BCVA (best-corrected visual acuity) and slit lamp examination (with special focus on cornea); window for exams is up to 3 days prior to dosing.
- On initial (first infusion) dosing day, vital signs must be assessed at pre-dose (within 30 minutes prior to SOI), +10 minutes and +30 minutes (±5 min) after SOI, EOI, and 1 hour post EOI. On subsequent dosing days, vital signs must be assessed at pre-dose (within 30 minutes prior to SOI), +30 minutes after SOI, and EOI. The Sentinel Subject must be observed for at least 24 hours post EOI. **On days where vital sign timepoints align with PK sampling timepoints, vital signs should be assessed prior to PK samples being drawn.**
- If completed within 72 hrs prior to the first dose, this assessment need not be repeated on Day 1 of Cycle 1. Refer to Table 15 of the protocol for comprehensive list of lab tests.

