- Troponin will be measured at the local lab (troponin I or T) and a central lab (troponin I). CK-MB at the local lab or if not possible by a central laboratory.
- BNP to be measured locally, or if not available by a central laboratory, at screening; if cardiac workup is required due to safety concerns during the study, BNP should be measured.
- Perform only in women of child-bearing potential. A serum pregnancy test should be performed at screening, and subsequent pregnancy tests may be either serum or urine;
- Final pregnancy test (serum or urine) must be performed in women of childbearing potential 60 days after last study treatment.
- On dosing days, ECG to be performed in triplicate at predose (within 30 minutes prior to SOI) and EOI. **On days where ECG timepoints align with PK sampling timepoints, ECGs should be performed prior to PK samples being drawn (PK sample should be taken at the exact nominal time; refer to footnote 21).** At screening, on interim visits (C1D8 and C1D15) and End of Study obtain a single ECG measurement.
- At Screening, LVEF may be performed within 30 days prior to first dose. All ECHOs indicated on dosing days may be performed up to 5 days before dosing. All ECHOs to be done locally and sent to GSK for central imaging storage.
- May be performed up to 21 days prior to C1D1 as screening value. Needs to be performed by the same method throughout the study as was done at baseline (i.e. if PET scan was used as baseline, subject needs to be followed by PET scans). Selected target lesion needs to be measured and followed over time.
- Samples from within 14 days prior to first dose are acceptable.
- Sample(s) collected for analysis by central lab. The same sample will be used for BCMA (flow) and PD during Screening. On D8 only postdose PD assessment will be performed

16. FISH testing at least for: t(4;14), t(14;16), 17p13del. FISH results from samples taken within 60 days prior to first dose are acceptable.
17. Archival tissue from up to 60 days prior to study is acceptable
18. A single sample for sBCMA will be collected at C1D8, C1D15 and at the End of Study visit. sBCMA samples will also be collected on C1D1 at predose (within 30 minutes prior to SOI), at EOI (± 5 minutes) and on C1D2 24h post SOI. On C2D1 sBCMA will be collected pre-dose (within 30 minutes prior to SOI) and at the EOI (± 5 minutes)

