16.4.2. Treatment Emergent Flag for Adverse Events

Flag	Definition
Treatment Emergent	
 • Study Treatment Start Date \leq AE Start Date • AE Start Date is missing

NOTES:

- If the study treatment stop date is missing, then the AE will be considered to be On-Treatment.
- Time of study treatment dosing and start/stop time of AEs should be considered, if collected.

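### Section 16.4.1 labels every Day 1 ECG and vital-sign record Pre-Treatment, including those taken after the first infusion starts, and the SAP does not say whether they count in the worst-case post-baseline tables

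*SAP*

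**What the plan says.** **Phase.** The table in Section 16.4.1 defines Pre-Treatment as "Date ≤ Study Treatment Start Date" and On-Treatment as "Study Treatment Start Date < Date". Neither definition uses clock time. The text below it names the domains: "The first dosing day (Day 1) is considered Pre-Treatment for ECOG, ECG, vital signs, liver events, lab tests, cardiac scan, and other safety domains". Two domains go the other way: "The first dosing day (Day 1) is considered to be On-Treatment for adverse events and concomitant medications". The only instruction to use clock time is in Section 16.4.2 and concerns adverse events: "Time of study treatment dosing and start/stop time of AEs should be considered, if collected".

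**Schedule.** For Part 1 (Section 16.2.2.1) the ECG footnote reads "On dosing days, ECG to be performed in triplicate at predose (within 30 minutes prior to SOI) and EOI". The vital-sign footnote for the first infusion day begins "vital signs must be assessed at pre-dose (within 30 minutes prior to SOI), +10 minutes and +30 minutes" and goes on to add EOI and one hour after EOI. The Part 2 myeloma schedule (16.2.3.1) and the Part 2 lymphoma schedule (16.2.3.3) set the same time points.

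**Baseline.** Section 5.2 takes the last non-missing value before dosing; for ECG it averages the baseline triplicate. It then adds: "If time is not collected, Day 1 assessments are assumed to be taken prior to first dose and used as baseline".

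**Displays.** Section 8.7 restricts the QTc grade-increase and QTc change categories to the worst post-baseline value. The heart-rate, diastolic blood-pressure and temperature tables in Section 16.12.8 carry the same restriction, as do two of the four systolic tables.

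**The concern.** A record taken during or after an infusion is not a pre-treatment record. Section 16.4.1 calls it one because it shares a calendar date with the first dose. Section 5.2 asks whether the record precedes the dose, and answers differently for the same record.

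Safety is part of the primary objective (Section 2.2), and Section 8.2 describes the trial as first time in human and lists infusion-related reactions among its events of interest. The records in question are those taken around the first infusion. The exposure-response dataset specification in Section 16.10.1 uses the model-predicted Cycle 1 EOI concentration as the first-dose maximum of the conjugate, so the Day 1 EOI ECG sits at the time point the SAP itself treats as peak first-dose exposure. For a subject who receives a single dose, these are the only infusion-time ECG and vital signs.

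There is also a mismatch between domains. A reaction starting during the first infusion is On-Treatment as an adverse event, while the blood pressure and heart rate measured during it are Pre-Treatment.

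**Working it through.** The plan gives no figure to reproduce. The check applies the date rule of Section 16.4.1 to the Day 1 time points of the three-weekly schedules (weekly dosing was not explored), then compares the result with Section 5.2.

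| Cycle 1 Day 1 record | After start of infusion? | Phase under 16.4.1 | Baseline under 5.2, time recorded | Baseline under 5.2, time not collected |
|---|---|---|---|---|
| ECG, pre-dose | No | Pre-Treatment | Yes | Candidate |
| ECG, EOI | Yes | Pre-Treatment | No | Candidate |
| Vital signs, pre-dose | No | Pre-Treatment | Yes | Candidate |
| Vital signs, 10 min | Yes | Pre-Treatment | No | Candidate |
| Vital signs, 30 min | Yes | Pre-Treatment | No | Candidate |
| Vital signs, EOI | Yes | Pre-Treatment | No | Candidate |
| Vital signs, 1 h after EOI | Yes | Pre-Treatment | No | Candidate |

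**Counts per subject.**
- ECG: 2 scheduled Day 1 time points, 1 of them after the infusion starts (1/2 = 50%). In tracings this is 3 of 6 when both time points are triplicate.
- Vital signs: 5 scheduled time points, 4 of them after the infusion starts (4/5 = 80%).
- On-Treatment under the rule as written: 0 of 2 and 0 of 5.
- On-Treatment if assigned by time or planned time point: 1 of 2 and 4 of 5.

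**Time recorded.** The EOI ECG is later than baseline under Section 5.2, so it is post-baseline. Under Section 16.4.1 it is Pre-Treatment. Whether it enters a worst-case post-baseline table depends on which definition selects the records. Neither Section 8.7 nor the display list says. Two programmers following the text could build different tables.

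**Time not collected.** The assumption in Section 5.2 covers Day 1 assessments without reference to planned time point. A post-infusion value could then serve as baseline, and later changes would be measured from it.

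**Other domains.** Footnote 1 of each schedule puts dosing-day assessments before drug administration unless stated otherwise, and no post-dose Day 1 safety laboratory sample or ECOG assessment is scheduled. The Day 1 rule fits those domains.

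**The case against.** The strongest reply is that Section 16.4.1 only attaches a label. The worst-case displays are worded as post-baseline, not on-treatment, and no display is said to be filtered by phase. A timed EOI record comes after the pre-dose baseline and would qualify. This stands in part: loss from those tables is possible but not stated. It does not defend the label, and it leaves open which of the two sections governs.

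A reader might go further and infer three things that the SAP does not support:

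- **That Day 1 EOI ECGs drop out of the concentration-QTc plots.** Section 12.2 calculates the change for each ECG and merges it with time-matched concentrations, with no phase filter. A pharmacokinetic sample is scheduled at Day 1 EOI, so the pair can be formed.
- **That post-infusion values generally become baseline.** This needs assessment time to be uncollected. Nothing shows that ECG or vital-sign times are missing, and Section 16.5.2 uses planned time relative to dosing in summaries and shows planned and actual times in listings. The size of any resulting baseline shift cannot be taken from the document.
- **That the first-infusion safety signal is lost.** Day 1 is On-Treatment for adverse events, infusion-related reactions have their own summaries, by-visit summaries of vital signs and ECG values are planned, and values of potential clinical importance are listed.

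**Conclusion.** The rule is wrong as written for ECG and vital signs. In every treated subject it labels 1 of 2 scheduled Day 1 ECG time points and 4 of 5 vital-sign time points Pre-Treatment although the infusion has started, and it conflicts with the pre-dose definition of baseline in Section 5.2. These counts rest only on the schedules and assume that the scheduled assessments were done.

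The consequences are conditional. Omission from the worst-case post-baseline QTcF and vital-sign tables follows if the phase variable selects records. Use as baseline follows only where time was not collected. No change in a reported result is demonstrated, and the concentration-QTc plots, listings and adverse event summaries are not shown to be affected. This is a should-fix point: the text needs correcting because it leaves primary-safety tables open to two constructions, not because a loss of data has been established.

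**What to change.** 1. In Section 16.4.1, assign Day 1 ECG and vital-sign records by date and time or, if time is missing, by planned time point: pre-dose is Pre-Treatment, and any time point after the start of infusion is On-Treatment.
2. In Section 5.2, limit the missing-time assumption to records whose planned time point is pre-dose or not given.
3. In Section 8.7, state that worst-case post-baseline summaries include the Day 1 post-dose ECG and vital signs.
4. Leave the Day 1 rule for laboratory tests and ECOG unchanged.

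The cost is a sentence in each of three sections and a small programming change. No new data are needed, since the schedules define these assessments by time relative to infusion and Section 16.5.2 already relies on planned time. If tables have been produced, the worst-case QTcF and vital-sign displays should be checked to see which definition was applied.

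### The concomitant-medication End flag tests the start date and the on-therapy period has no end, so the summaries drop drugs the SAP means to include and cannot exclude post-therapy drugs as it requires

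*SAP*

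**What the plan says.** SAP 16.4.1 defines On-Treatment as "Study Treatment Start Date < Date" and lists no later phase. A note adds: "The first dosing day (Day 1) is considered to be On-Treatment for adverse events and concomitant medications". That note moves the lower bound by a day and says nothing about an upper one.

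Section 16.4.1.1 then derives two flags.

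- **Start flag.** After the BEFORE test it reads: "Else assign to 'DURING' if the start date falls into the on-therapy period as defined above". Ongoing subjects and missing start dates also go to DURING. The remainder follows: "Else assign to 'AFTER' if start date is after the on-therapy period".
- **End flag.** The first clause is: "Assign to 'BEFORE' if end date is prior to study treatment start date". The second is: "Else assign to 'DURING' if start date falls into the on-therapy period or if subject is ongoing". It also takes a missing end date when the start flag is not AFTER. The third clause opens with the same words as the start flag's AFTER clause and adds a missing end date when the start flag is AFTER.

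The main summary keeps records with Start in BEFORE or DURING and End in DURING or AFTER. Its stated purpose is to include drugs begun before treatment that have a "missing end date or end date after study treatment start date", and to leave out drugs begun post-therapy. For the on-therapy-onset summary the text repeats the exclusion: "any medication that was started during post-therapy (see above for definition of post-therapy) will be excluded". Section 6.6 requires only that a concomitant medication was used at some time within the on-therapy window.

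**The concern.** Only the End flag's BEFORE clause looks at the end date. Its DURING and AFTER clauses look at the start date, so a drug begun before treatment can satisfy them only through the side conditions (subject ongoing, or end date missing). If neither applies, no clause catches it. The selection rule is written as programmable logic, so a blank flag means the record is silently excluded.

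The second problem is independent of the first. A period with no end has nothing after it, so the AFTER category is empty and the post-therapy exclusion has nothing to act on. The definition of post-therapy said to stand above appears in neither 16.4.1 nor 16.4.1.1.

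At stake is whether the concomitant-medication tables describe what they claim to describe, and whether two programmers working from this text would produce the same tables.

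**Working it through.** No sample size or error rate is involved. The check traces the flags and the selection rule as written.

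**Inputs.** The period definition and Day 1 note (16.4.1); the start flag, End flag and selection rule (16.4.1.1); the stated intent (16.4.1.1 and 6.6).

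**Trace of the key case.** A drug starts before treatment and has a recorded stop date on or after treatment start. The subject's discontinuation records are complete.

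1. Start flag: the start precedes treatment, so BEFORE.
2. End flag, BEFORE: the stop date is not before treatment start, so false.
3. End flag, DURING: the start date is not on-therapy, the subject is not ongoing and the end date is present, so false.
4. End flag, AFTER: the start date is not after therapy and the end date is present, so false.
5. The End flag is unassigned. Selection requires DURING or AFTER, so the record is excluded.

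**All patterns, discontinued subject.** Each cell gives Start flag / End flag and whether the record is in or out of the main summary.

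| Drug start → stop | As written | End date tested only | Upper bound only | Both changes | Stated intent |
|---|---|---|---|---|---|
| before → before | BEFORE/BEFORE, out | out | out | out | out |
| before → during | BEFORE/none, **out** | BEFORE/DURING, in | BEFORE/none, **out** | BEFORE/DURING, in | in |
| before → after | BEFORE/none, **out** | BEFORE/DURING, in | BEFORE/none, **out** | BEFORE/AFTER, in | in |
| before → missing | BEFORE/DURING, in | in | in | in | in |
| during → any | DURING/DURING, in | in | in | in | in |
| after → after or missing | DURING/DURING, **in** | DURING/DURING, **in** | AFTER/AFTER, out | AFTER/AFTER, out | out |

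Bold marks disagreement with the stated intent. Each change repairs one side only, and both are needed to match the intent in every row.

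**Ongoing subject.** The before → during record becomes BEFORE/DURING and is kept through the ongoing clause. The same record therefore leaves the table once discontinuation is recorded, although the drug history has not changed.

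**Which summaries each fault reaches.** The on-therapy-onset and blood-product summaries take only records with Start = DURING. Pre-treatment starts are outside them by design, so they are affected only by the missing upper bound. The main concomitant-medication summary is affected by both faults.

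**Partial stop dates.** Section 16.7.2.1 imputes these for concomitant medications, so once imputed they count as present and do not escape the gap.

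**The case against.** The strongest reply is that the intent is plain. Section 16.4.1.1 states in words which drugs belong, 6.6 agrees, and the End flag's own BEFORE clause tests the right date. A competent programmer would probably notice the slip. That is fair as to cause, but it does not remove the contradiction: the algorithm and the prose give different tables and the SAP does not say which governs. The missing upper bound cannot be repaired by reading for intent, because the length of the window is not stated.

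Four stronger readings are tempting, and the document does not support them.

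- **A count of lost drugs per subject.** Assuming 10 long-term drugs per subject and recorded stop dates for 20% to 50% of them, one would get 10 × 0.20 = 2 to 10 × 0.50 = 5. Neither input is in the document. Section 6.6 also counts a subject once per ingredient, so a lost record changes nothing if another record of that ingredient qualifies.
- **That no subject is ongoing when the tables are made.** This is a reasonable expectation for Table 1.0213 (lymphoma, planned at up to 10 subjects in 2.3), the only one of the four in the end-of-study display list. Tables 1.0210 to 1.0212 belong to the earlier myeloma package. Section 6.2 provides for subjects still on treatment, and the ongoing clause keeps their records.
- **That drugs begun long after the last dose are counted.** This depends on how long concomitant medications are collected, which is a protocol matter. The exclusion cannot operate as written, but how much it would have excluded is unknown.
- **That the adverse-event flag in 16.4.2 needs the same bound.** Nothing here shows that flag to be wrong. Bounding it could remove late-onset events from a study that was amended to extend ocular follow-up.

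It is also true that only descriptive tables are affected and that concomitant-medication listings (1.0620, 1.0621) are planned for both cohorts.

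**Conclusion.** The point holds. As written, 16.4.1.1 leaves the End flag blank for drugs begun before treatment and stopped on a recorded date on or after treatment start, in subjects whose discontinuation records are complete. Those records fall out of Tables 1.0210 to 1.0213, contrary to the section's own statement and to 6.6. Independently, AFTER cannot be assigned by date, so the post-therapy exclusion has no effect in the concomitant-medication, on-therapy-onset and blood-product summaries.

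The conclusion assumes that the rules are programmed literally. The number of records affected cannot be determined from the document. PFS, TTP and response use separately handled anti-cancer therapy dates, and no efficacy, DLT or adverse-event result depends on these flags. It is a definite error in the specification with limited consequences, and it should be corrected. The end-of-study RAP (section 2) leaves the data-handling conventions unchanged, so the fault carries into that deliverable too.

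**What to change.** 1. In the End flag, replace the start date by the end date in the DURING and AFTER clauses, keeping the provisions for ongoing subjects and missing end dates.
2. In 6.6 and 16.4.1.1, for concomitant medications and blood products only, state when the on-therapy period ends, in line with the protocol, and define post-therapy as after that point. The sponsor must supply the window, because the SAP gives none.
3. Leave the treatment-emergent flag in 16.4.2 as it is.
4. Check whether the existing program follows the printed algorithm or the stated intent. Re-run the flags and, where they change, Tables 1.0210 to 1.0213, any on-therapy-onset summary, and the blood-product summaries (1.0480 to 1.0483 and 1.0490 to 1.0493).

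The cost is a few words of SAP text and one derivation to re-run. No new data are needed.
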